8.2.3 Rationale for Primary Endpoints

The primary endpoint of this study is to assess the safety and tolerability of LOXO-292. LOXO-292 has already been administered to healthy subjects (LOXO-RET-18014 and LOXO-RET-18015) at a single dose level of 160 mg. As a dose-exposure analysis in cancer patients (LOXO-RET-17001) indicated that a reduction in clearance led to greater than proportional increases in LOXO-292 exposure with increases in LOXO-292 doses, this study

will investigate the safety and tolerability of higher doses (i.e., potential therapeutic and supratherapeutic doses) of LOXO-292 when administered to healthy subjects. Ascending doses up to and possibly including 720 mg will be investigated. The safety endpoints in the study are deemed adequate to detect any safety signals when these higher doses of LOXO-292 are administered to healthy subjects.

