9.2 Endpoints

Safety:

Safety endpoints will include AEs including the subject incidence, number, and severity of TEAEs following single oral doses of LOXO-292 in healthy adult subjects and safety markers for 12-lead ECGs, physical examinations, vital signs, and clinical laboratory tests.

Pharmacokinetics:

The plasma PK endpoints will include AUC0-t, AUC0-24, AUC0-inf, AUC%extrap, CL/F, Cmax, Tmax, Kel, t_{1/2}, and Vz/F.

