13.2.6 Adverse Events

13.2.6.1 Adverse Event Definition

An AE means any untoward medical occurrence associated with the use of a drug in humans, whether or not considered drug related.

A suspected adverse reaction means any AE for which there is a reasonable possibility that the drug caused the AE. Reasonable possibility means there is evidence to suggest a causal relationship between the drug and the AE.

An AE can therefore be any unfavorable and unintended sign (including an abnormal laboratory finding), symptom, or disease temporally associated with the use of a medicinal (investigational) product, whether or not related to the medicinal (investigational) product.

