13.2.6.3 Reporting

AEs and SAEs will be collected beginning at informed consent. AEs will be recorded throughout the study (i.e., from signing of the ICF until EOS or ET if the subject discontinues and does not complete a follow up call), either as subject medical history (if the event is reported as beginning prior to signing of the ICF or if the event occurs prior to study drug administration on Day 1 and is assessed as not related to study procedures by the PI [or designee]) or as AEs (if the event occurs after signing of the ICF but prior to study drug administration on Day 1 and is assessed as related to study procedures by the PI [or designee], or if the event occurs after study drug administration on Day 1 through EOT or ET regardless of relationship to study drug). From EOT or ET through EOS, only AEs assessed as related to study drug by the PI (or designee) are to be reported. All SAEs that develop from the time of ICF signing until EOS (or ET, if subject discontinues from the study and does not complete the follow up call) are to be reported.

Unless a subject withdraws consent or is withdrawn from the study and does not complete the follow up call, all subjects must be followed until the EOS. AEs which are ongoing at the EOS which are assessed as related to study drug may be continued to be followed until the symptoms or value(s) return to normal, or acceptable levels, as judged by the PI or designee and confirmed by the Sponsor. The PI (or designee) should use appropriate judgment in ordering additional tests as necessary to monitor the resolution of events. The Sponsor may request that additional safety tests be performed.

The PI or designee will review each AE and assess its relationship to drug treatment (yes [related] or no [unrelated]).

Unrelated	The time course between the administration of study drug and the occurrence or worsening of the AE rules out a causal relationship and another cause is suspected
-----------	-------------------------------------------------------------------------------------------------------------------------------------------------------------------

Related	The time course between administration of study drug and the occurrence or worsening of the AE is consistent with a causal relationship and no other cause can be identified

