---------	------------------------------------------------------------------------------------------------------------------------------------------------------------------------------

Each sign, symptom, or abnormal laboratory value reported as an AE will be graded on the National Cancer Institute (NCI) Common Terminology Criteria for Adverse Events (CTCAE) version 5.0 toxicity grading scale. Only abnormal clinical laboratory results or other events deemed to be clinically significant by the PI or designee will be recorded in the database as AEs and will be graded utilizing CTCAE guidelines.

Grade refers to the severity of the AE. The CTCAE displays Grades 1 through 5 with unique clinical descriptions of severity for each AE based on the following general guideline ([NCI CTCAE 27 Nov 2017](#)):

Grade 1	Mild; asymptomatic or mild symptoms; clinical or diagnostic observations only; intervention not indicated.
Grade 2	Moderate; minimal, local or noninvasive intervention indicated; limiting age-appropriate instrumental ADL*.
Grade 3	Severe or medically significant but not immediately life threatening; hospitalization or prolongation of hospitalization indicated; disabling; limiting self-care ADL**.
Grade 4	Life-threatening consequences; urgent intervention indicated.
Grade 5	Death related to AE.

A Semi-colon indicates 'or' within the description of the grade.

Note: Not all grades are appropriate for all AEs. Therefore, some AEs are listed within the CTCAE with fewer than 5 options for grade selection. Grade 5 (death) is not appropriate for some AEs and therefore is not an option.

ADL=Activities of Daily Living

* Instrumental ADL refer to preparing meals, shopping for groceries or clothes, using the telephone, managing money, etc.

** Self care ADL refer to bathing, dressing and undressing, feeding self, using the toilet, taking medications, and not bedridden.

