14.3.1 Safety Analyses

All safety data will be populated in the individual CRFs. All safety data will be listed by subjects.

Dosing dates and times will be listed by subject.

AEs will be coded using the Medical Dictionary for Regulatory Activities (MedDRA[®]) and summarized by treatment for the number of subjects reporting the TEAE. A by-subject AE data listing including verbatim term, coded term, treatment, severity, and relationship to treatment will be provided.

Safety data including ECGs, physical examinations, vital signs assessments, clinical laboratory results, will be summarized by treatment and point of time of collection.

Descriptive statistics using appropriate summary statistics will be calculated for quantitative safety data as well as for the difference to baseline, when appropriate.

Concomitant medications will be listed by subject and coded using the World Health Organization drug dictionary. Medical history will be listed by subject.

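### Read literally, Section 13.2.6.3 lets only events judged clinically significant be recorded as AEs, which conflicts with the protocol's AE definition and could lower TEAE counts

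*Protocol*

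**What the plan says.** Section 13.2.6.1 defines an AE broadly: "An AE means any untoward medical occurrence associated with the use of a drug in humans, whether or not considered drug related". It then extends this to "any unfavorable and unintended sign (including an abnormal laboratory finding), symptom, or disease temporally associated" with use of the product. Neither sentence sets a threshold of clinical significance.

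Section 13.2.6.3 first gives a recording rule by time period. An event counts as an AE "if the event occurs after study drug administration on Day 1 through EOT or ET regardless of relationship to study drug". This rule has no significance threshold either.

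Later in the same section, just before the grading scale, comes the restriction on what is entered and CTCAE-graded as an AE: "Only abnormal clinical laboratory results or other events deemed to be clinically significant by the PI or designee will be recorded in the database". The scale that follows opens with Grade 1: "Mild; asymptomatic or mild symptoms; clinical or diagnostic observations only; intervention not indicated".

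On use of the data, Section 8.2.3 says: "The primary endpoint of this study is to assess the safety and tolerability of LOXO-292". Section 9.2 lists the measures: "Safety endpoints will include AEs including the subject incidence, number, and severity of TEAEs following single oral doses of LOXO-292", followed by ECGs, physical examinations, vital signs and laboratory tests. Under Section 14.3.1, AEs are coded and "summarized by treatment for the number of subjects reporting the TEAE".

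**The concern.** Requiring clinical significance before a laboratory abnormality becomes an AE is ordinary practice and is not the problem. The problem is that the sentence goes on to cover other events, with nothing to confine that phrase to objective findings. A mild headache or dry mouth that the investigator considers not clinically significant is an AE under Section 13.2.6.1 and under the first rule of Section 13.2.6.3, yet the later sentence keeps it out of the database. Site staff cannot follow both instructions.

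The main output on tolerability is a count of subjects with each TEAE in cohorts of 6. A filter that acts before data entry cannot be reversed by any analysis plan. The study is open-label (Section 12.4), so whoever applies the filter knows the dose. Mild symptoms are also foreseeable: Section 8.1.1 lists nausea, loose stools, taste change and dry mouth among the theoretical risks.

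**Working it through.** The protocol gives no event rate, power or other figure for this point, so there is nothing to reproduce. The check is textual, with simple arithmetic on what one lost event means.

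**Step 1: the same event under each rule.** Take a mild symptom after dosing, before discharge, judged not clinically significant.

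| Place | Is it an AE in the database? |
|---|---|
| 13.2.6.1, definition | It is an AE; symptoms are named and no threshold is set |
| 13.2.6.3, rule by time period | Yes, recorded as an AE |
| 13.2.6.3, sentence before the grading scale | No, unless clinically significant |

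The third row contradicts the first two. The clauses about relationship to drug in 13.2.6.1 and 13.2.6.3 concern causality, not significance. The conflict therefore rests on the breadth of the definition and the unfiltered recording rule.

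**Step 2: direction.** Let p be the chance that a subject has a TEAE and s the share of such subjects still counted after the filter, with s between 0 and 1. Recorded incidence is p × s, which is at most p. The filter can lower incidence and number or leave them unchanged; it cannot raise them. If it removes mainly Grade 1 events, those that remain look more severe on average.

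**Step 3: the weight of one subject.** Section 10.1 plans 6 subjects per cohort. A subject whose only event is dropped lowers cohort incidence by 1/6 = 0.167, or 16.7 percentage points.

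**Step 4: illustration only.** The documents give neither p nor s, so both are assumed. The chance that a cohort of 6 shows at least one subject with a recorded TEAE is 1 − (1 − p × s)^6. For example, p = 0.2 and s = 0.5 give 1 − 0.9^6 = 0.469.

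| Assumed p | s = 1 (no filtering) | s = 0.75 | s = 0.5 | s = 0.25 |
|---|---|---|---|---|
| 0.1 | 0.469 | 0.374 | 0.265 | 0.141 |
| 0.2 | 0.738 | 0.623 | 0.469 | 0.265 |
| 0.3 | 0.882 | 0.783 | 0.623 | 0.374 |
| 0.5 | 0.984 | 0.940 | 0.822 | 0.551 |

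The s = 1 column applies to symptoms if the sentence was meant for objective findings only.

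**Step 5: is there a backup?** Section 14.3.1 summarises laboratory results, vital signs, ECGs and physical examinations by treatment and time, whatever their AE status. Symptoms have no such summary. A symptom treated with the permitted acetaminophen would leave a trace in the concomitant-medication listing, but an untreated one would not.

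**The case against.** The strongest reply is that only objective findings were meant. Section 13.2.6.2 attaches clinical significance to a list of abnormal laboratory values, vital signs and ECGs, and the other events of Section 13.2.6.3 may be shorthand for that list. The sentence just before the restriction speaks of grading each sign, symptom or laboratory value reported as an AE, without a significance test. Keeping a Grade 1 for asymptomatic or mild events also suggests that mild events were expected in the database. So do the escalation rules in Section 12.4.1, which apply their own significance test to Grade 3 or higher toxicity; that test would be largely redundant if every recorded AE had already passed one.

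This is a plausible account of intent, and it stands as a reason not to claim that symptoms will be lost. It does not remove the conflict. The sentence does not name the three categories that Section 13.2.6.2 names, and the preceding sentence grades only what has already been reported as an AE.

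The consequences are also bounded. The toxicity triggers in Section 12.4.1 need a clinically significant Grade 3 or higher event or a drug-related SAE, so dropping mild events would not change them. The protocol specifies no inferential comparison of AE rates between cohorts. Both points stand; what remains exposed is the descriptive TEAE profile by dose.

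**Conclusion.** The contradiction is on the page and needs no assumption. That the filter can only lower TEAE incidence and number, or leave them unchanged, follows from its form. Whether it lowers them depends on how the site reads the sentence. The effect on symptoms is nil under the narrower reading, and otherwise its size cannot be derived from the documents. The one firm figure is 16.7 percentage points of cohort incidence for each subject whose only event is dropped.

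A reader might infer more, and the documents do not support it:

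- **That downward bias is demonstrated, or differs by cohort.** It is possible; nothing shows that it would occur or vary with dose.
- **That TEAE incidence is the primary endpoint.** Section 8.2.3 names safety and tolerability; Section 9.2 lists TEAEs first among several measures.
- **That LOXO-RET-18015 shows how much would be lost.** Section 8.2.2 lists six drug-related event types from that study, four of them Grade 1. Three of those four (ALP, ALT, AST) are laboratory values that an ordinary significance filter would still screen; only dyspepsia is a symptom. That study's recording rule is not shown.

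This is a data-capture rule fixed in the protocol, so an analysis plan cannot repair it. It merits correction as an inexpensive clarification.

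**What to change.** Reconcile the sentence in Section 13.2.6.3 with Sections 13.2.6.1 and 13.2.6.2 by limiting the filter to objective findings. Suggested text:

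> *Abnormal laboratory, vital-sign or ECG findings will be recorded as AEs only if deemed clinically significant; all other untoward signs and symptoms will be recorded and graded as AEs.*

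Put the same rule in the CRF completion instructions. If the narrower meaning was always intended, this only states it. The cost is one sentence in the protocol, a matching CRF instruction, and a few more mild AEs to enter and code.

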13.2.6.4 Serious Adverse Event

If any AEs are serious, as defined by the Food and Drug Administration (FDA) Code of Federal Regulations (CFR), Title 21, special procedures will be followed. All SAEs will be reported to the Sponsor or designee via fax or e-mail within 24 hours of first awareness of the event, whether or not the serious event(s) are deemed drug-related. All serious event reporting will adhere to 21 CFR 312.32 for Investigational New Drugs (IND) and to the Guidance for Industry and Investigators: Safety Reporting Requirements for INDs and BA/BE, dated December 2012. Any event that meets the criteria of a suspected unexpected serious adverse reaction (SUSAR) will be reported to the Institutional Review Boards/ Independent ethics

committee (IRB/IEC) according to site/CRU policy by the Investigator (or designee) and to regulatory authorities by the Sponsor (or Sponsor designee) according to regulatory authority requirements. Refer to Reference Safety Information (RSI) in the current IB for expected adverse reactions.

A SAE is any AE or suspected adverse reaction that in the view of either the PI (or designee) or Sponsor, results in any of the following outcomes: Death, a life-threatening AE, inpatient hospitalization or prolongation of existing hospitalization, a persistent or significant incapacity or disability, or a congenital anomaly/birth defect. Important medical events that may not result in death, be life-threatening, or require hospitalization may be considered serious when, based upon appropriate medical judgment, they may jeopardize the patient or subject and may require medical or surgical intervention to prevent one of the outcomes listed in the above definition. Examples of such medical events include allergic bronchospasm requiring intensive treatment in an emergency room or at home, blood dyscrasias or convulsions that do not result in inpatient hospitalization, or the development of drug dependency or drug abuse.

Life-threatening is defined as an AE or suspected adverse reaction that in the view of the PI (or designee) or Sponsor, places the patient or subject at immediate risk of death. It does not include an AE or suspected adverse reaction that, had it occurred in a more severe form, might have caused death.

All SAEs must be reported on a SAE Report Form provided by Loxo Oncology and sent by fax or e-mail to the Sponsor listed in [Section 3](#) within 24 hours of first awareness of the event.

When using the SAE efax (+ 1 [contact]) a cover page including study identification number and study drug product (i.e., LOXO-292) is required. Alternatively, an email can be sent to [contact].

The PI is not obligated to actively seek information regarding the occurrence of new SAEs beginning after EOS. However, if the PI learns of such an SAE, and that event is deemed associated with the use of study drug, he/she should promptly document and report the event.

The PI will be requested to supply detailed information as well as follow-up regarding the SAE. Although not considered an AE per se, the Sponsor must be notified of any subject or subject's partner who becomes pregnant during the study at any time between Screening until 90 days after study drug administration on Day 1.

13.3 Pharmacokinetic Assessments

13.3.1 Blood Sampling and Processing

For all subjects, blood samples for the determination of LOXO-292 will be collected at scheduled time points as delineated in the Study Events Flow Chart ([Section 6](#)). Tubes will be identified with a barcode using an appropriate label.

Instructions for blood sampling, collection, processing, and sample shipment will be provided separately.

Blood collections performed outside of the sample collection windows as defined in the Study Events Flow Chart ([Section 6](#)) will be considered deviations.

13.3.2 Future Analyses

Any residual plasma from the PK samples may be stored by the Sponsor or Bioanalytical facility for up to 5 years following dosing of the last cohort and may be used for future analyses of plasma for metabolite(s) formation. Tubes will be identified with a barcode using an appropriate label. No diseases/conditions, deoxyribonucleic acid, or ribonucleic acid will be the focus of these analyses. The analyses will focus on assessing potential metabolites. Any additional research on these samples unspecified by this protocol will require approval from the subjects. Samples will not be submitted to a public database.

The sponsor and contract research organizations involved in the clinical conduct, bioanalytical analyses and pharmacokinetics and statistical analysis of the data will have access to the samples and/or the data that resulted from the analysis, if performed.

By signing the ICF, subjects agree to the possible future analysis of these samples; however, at any time, the subjects can contact the CRU staff to request destruction of the residual samples after the LOXO-292 PK assessments required to meet the primary objective of the study are completed.

13.3.3 Pharmacokinetic Parameters

PK parameters for plasma LOXO-292 will be calculated as follows, as appropriate:

AUC0-t: The area under the concentration-time curve, from time 0 to the last observed non-zero concentration, as calculated by the linear trapezoidal method.

AUC0-24: The area under the concentration-time curve, from time 0 to Hour 24, as calculated by the linear trapezoidal method. If the 24-hour plasma concentration is missing, BLQ or not reportable, then this parameter cannot be calculated.

AUC0-inf: The area under the concentration-time curve from time 0 extrapolated to infinity. AUC0-inf is calculated as the sum of AUC0-t plus the ratio of the last measurable plasma concentration to the elimination rate constant.

AUC%extrap: Percent of AUC0-inf extrapolated, represented as $(1 - AUC0-t/AUC0-inf) * 100$.

CL/F: Apparent total plasma clearance after oral (extravascular) administration, calculated as Dose/AUC0-inf.

Cmax: Maximum observed concentration.

Tmax: Time to reach Cmax. If the maximum value occurs at more than one time point, Tmax is defined as the first time point with this value.

Kel: Apparent first-order terminal elimination rate constant calculated from a semi-log plot of the plasma concentration versus time curve. The parameter will be calculated by linear least-squares regression analysis using the maximum number of points in the terminal log-linear phase (e.g., three or more non-zero plasma concentrations).

t_{1/2}: Apparent first-order terminal elimination half-life will be calculated as 0.693/Kel.

Vz/F: Apparent volume of distribution during the terminal elimination phase after oral (extravascular) administration, calculated as (Dose/AUC_{0-inf}) x Kel.

No value for Kel, AUC%extrap, AUC_{0-inf}, CL/F, Vz/F, or t_{1/2} will be reported for cases that do not exhibit a terminal log linear phase in the concentration time profile.

No PK parameters will be calculated for subjects with 2 or fewer consecutive time points with detectable concentrations.

Individual and mean plasma concentration time curves (both linear and log-linear) will be included in the final Clinical Study Report.

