7 ABBREVIATIONS

µM	Micromolar
AE	Adverse event
ALP	Alkaline phosphatase
ALT	Alanine aminotransferase
AST	Aspartate aminotransferase
AUC0-24	The area under the concentration-time curve, from time 0 to Hour 24
AUC%extrap	Percent of AUC0-inf extrapolated
AUC0-t	Area under the concentration-time curve, from time 0 to the last observed non-zero concentration (t)
AUC0-inf	Area under the concentration-time curve, from time 0 extrapolated to infinity
AV	Atrioventricular
BP	Blood pressure
BID	Twice daily
bpm	Beats per minute
BMI	Body mass index
CFR	Code of Federal Regulations
CL/F	Apparent total plasma clearance after oral (extravascular) administration
Cmax	Maximum observed concentration
CRF	Case report form
CRU	Clinical Research Unit
CTCAE	Common Terminology Criteria for Adverse Events
CYP	Cytochrome P450
ECG	Electrocardiogram
EOS	End of Study
EOT	End of Treatment
ET	Early Termination
FDA	Food and Drug Administration
FSH	Follicle-stimulating hormone
FU	Follow up

g	gram
GCP	Good Clinical Practice
GLP	Good Laboratory Practice
HBsAg	Hepatitis B surface antigen
HCV	Hepatitis C virus
hERG	Human ether-a-go-go related gene
HIV	Human immunodeficiency virus
HRT	Hormone replacement therapy
IB	Investigator's Brochure
IC ₅₀	Inhibitory concentration at 50%
ICF	Informed Consent Form
ICH	International Council on Harmonization
IND	Investigational New Drug
IRB	Institutional Review Board
IUD	Intrauterine device
Kel	Apparent terminal elimination rate constant
kg	Kilogram
LFT	Liver function test
m ²	Meter squared
MedDRA®	Medical Dictionary for Regulatory Activities®
mg	Milligram
mL	Milliliter
mmHg	Millimeter of mercury
msec	Millisecond
NCI	National Cancer Institute
ng	Nanogram
No.	Number
PCR	Polymerase chain reaction
PI	Principal Investigator
PK	Pharmacokinetic(s)
QA	Quality Assurance
QTc	Corrected value of the interval between the Q and T waves on the electrocardiogram tracing

RBC	Red blood cell
RET	Rearranged during transfection
RSI	Reference Safety Information
SAD	Single ascending dose
SAE	Serious adverse event
SAP	Statistical analysis plan
SUSAR	Suspected unexpected serious adverse reaction
TEAE	Treatment-emergent adverse events
Tmax	Time to reach maximum observed concentration
t½	Apparent terminal elimination half-life
US	United States
USA	United States of America
Vz/F	Apparent volume of distribution during the terminal elimination phase after oral (extravascular) administration
WBC	White blood cell

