As of August 24 2018, PK data were available from 141 patients (from the global Phase 1/2 study). LOXO-292 is absorbed after oral administration with a median time to maximum concentration (Tmax) of approximately 2 hours. Although the PK sampling of LOXO-292 was not long enough to adequately characterize AUC0-inf, the half-life appears to be 20 hours. Low concentrations of LOXO-292 were recovered as unchanged drug in urine indicating that the kidney contributes to overall clearance.

As of September 14, 2018, Loxo Oncology has initiated 16 single patient protocols, Special Access Scheme, or Temporary Authorization Use cases to provide access to LOXO-292 for patients with clinical need not meeting eligibility criteria for the ongoing global Phase 1/2 study. To date, no TEAEs have been attributed to study drug for these patients.

Preliminary PK data available from ongoing studies (LOXO-RET-18014 and LOXO-RET-18015) being conducted in healthy subjects indicate that LOXO-292 has an estimated terminal $t_{1/2}$ of approximately 24 hours after a single dose.

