8.2.2 Rationale for the Dose Selection and Dose Regimen

Single doses of 160 mg are currently being investigated in 2 studies in healthy volunteers in which Cmax have been preliminarily determined. LOXO-RET-18014 is a drug-drug interaction study evaluating the effects of itraconazole and rifampin on the PK of LOXO-292. In LOXO-RET-18015 the effects of food and of a proton-pump inhibitor (omeprazole) are being evaluated on the PK of LOXO-292. Preliminary Cmax data was reported for LOXO-292 following each study part and data when LOXO-292 was administered alone under fasted conditions in these studies are presented in [Table 1](#) (Data on file at the time of protocol development).

Table 1: Maximum concentration (Cmax) values following single dose LOXO-292 (160 mg) administered under fasting conditions

LOXO-292 Study Number	Part	Sample Size (n)	Cmax* (ng/mL)
LOXO-RET-18014	1	12	1656 ± 626 ng/mL
LOXO-RET-18014	2	12	1458 ± 626 ng/mL
LOXO-RET-18015	1	20	2223 ± 685 ng/mL

*Arithmetic mean (AM) ± standard deviation (SD)
Cmax = Maximum concentration (preliminary data), mL = milliliter, ng = nanogram

Single doses of greater than 160 mg have not been given to healthy subjects and the data from [Table 1](#) suggest the single-dose Cmax average value following dose level of 160 mg LOXO-292 is approximately 1800 ng/mL.

In a dose-exposure analysis in cancer patients who received doses of 20 mg once daily to 240 mg BID in the ongoing Phase 1/2 LOXO-RET-17001 Study, the CL/F of LOXO-292 decreased with increasing dose strength leading to greater than proportional increases in LOXO-292 exposure with increases in LOXO-292 doses. The steady-state Cmax of LOXO-292 in cancer patients treated with 160 mg BID, the currently recommended Phase 2 dose and dose planned for commercialization, is 3320 ± 1220 ng/mL (n=65, [Investigator's Brochure, Version 4, October 2018](#)). Based on the data from a single dose of 160 mg when administered to healthy subjects, the Cmax of a single dose of 320 mg (the dose selected for Cohort 1) is expected to be twice as high as from 160 mg i.e., approximately 3600 ng/mL, representing the therapeutic Cmax value expected in patients. The dose of 640 mg was selected for Cohort 2 as with linear PK, it is anticipated to produce a Cmax of approximately 6640 ng/mL, which is approximately twice as high as the Cmax seen in cancer patients treated with 160 mg BID LOXO-292 and would be considered the supratherapeutic exposure target.

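### Protocol Section 13.3.3 calculates Vz/F by multiplying Dose/AUC0-inf by Kel; an apparent volume requires division by Kel

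*Protocol*

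**What the plan says.** Protocol Section 13.3.3 gives a calculation rule for each plasma PK parameter. Three of them matter here:

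- CL/F: "Apparent total plasma clearance after oral (extravascular) administration, calculated as Dose/AUC0-inf".
- t1/2: "Apparent first-order terminal elimination half-life will be calculated as 0.693/Kel". Kel is described there as a first-order terminal rate constant from a semi-log regression.
- Vz/F: named as an apparent volume of distribution, "administration, calculated as (Dose/AUC_{0-inf}) x Kel".

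The abbreviations list in Section 7 also describes Vz/F as a volume: "Apparent volume of distribution during the terminal elimination phase after oral (extravascular) administration". Section 9.2 includes it among the PK endpoints ("CL/F, Cmax, Tmax, Kel, t_{1/2}, and Vz/F"), and the synopsis lists it too. No other section gives a formula for Vz/F. The clarification letter of 25 February 2019 concerns only an added ECG at 3.5 hours.

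**The concern.** The name and the formula do not describe the same quantity. A terminal-phase apparent volume is clearance divided by the terminal rate constant; the protocol multiplies them. The brackets close before the multiplication by Kel, so the line cannot be read as Dose divided by the product of AUC0-inf and Kel.

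If the line were programmed as written, every Vz/F value would be wrong, and by a factor that depends on each subject's own Kel. The error would therefore carry into comparisons between subjects and between dose levels. At fixed CL/F, a longer half-life means a larger true volume but a smaller printed value, so the direction reverses. This matters somewhat more in an ascending-dose study because Section 8.2.2 reports that in patients "the CL/F of LOXO-292 decreased with increasing dose strength". If volume were constant, such a fall in clearance would show up as a fall in Vz/F that did not happen.

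**Working it through.** **Inputs from the protocol.** The definitions of CL/F, Kel, t1/2, AUC0-inf and Vz/F are in Section 13.3.3. Section 8.1.1 gives the half-lives: in healthy subjects "of approximately 24 hours after a single dose", and in patients "the half-life appears to be 20 hours". The protocol states no numerical Vz/F, so there is no figure of its own to reproduce.

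**Step 1: units.** Take dose in mg, AUC in mg·h/L and Kel in 1/h.

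- CL/F = Dose/AUC0-inf: mg ÷ (mg·h/L) = L/h.
- As printed, CL/F × Kel: (L/h) × (1/h) = L/h².
- With division, (CL/F)/Kel: (L/h) ÷ (1/h) = L.

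Only the last is a volume. This step needs no assumption.

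**Step 2: relation of printed to correct value.** Printed/correct = (CL/F × Kel) ÷ ((CL/F)/Kel) = Kel².

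| Half-life | Kel = 0.693/t1/2 | 1/Kel², hours | 1/Kel², days |
|---|---|---|---|
| 24 h | 0.028875 per h (0.693 per day) | 1,199 | 2.08 |
| 20 h | 0.03465 per h (0.8316 per day) | 833 | 1.45 |

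The fold gap depends on the time unit because it compares quantities of different dimension. It shows that the number is wrong, but it is not a measure of importance.

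**Step 3: unit-free comparison of two subjects, 24 h against 20 h.**

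- Equal CL/F: true ratio 24/20 = 1.20; printed ratio 20/24 = 0.83. The distortion is (24/20)² = 1.44, and the direction reverses.
- Equal true volume: true ratio 1.00; printed ratio (20/24)² = 0.69.

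**Step 4: falling clearance at constant volume (assumed).** Kel is then proportional to CL/F, so the printed Vz/F is proportional to (CL/F)². The sizes of the fall are also assumed.

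| Assumed fall in CL/F | Printed Vz/F relative to start | Apparent fall in Vz/F (true fall 0%) |
|---|---|---|
| 10% | 0.9² = 0.81 | 19% |
| 20% | 0.8² = 0.64 | 36% |
| 30% | 0.7² = 0.49 | 51% |

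**Step 5: check against a known volume.** A one-compartment oral profile was generated for 320 mg (the Cohort 1 dose) at the 21 flow-chart times. AUC0-inf was calculated by the protocol's linear trapezoid plus Clast/Kel, with Kel from a log-linear fit to the last five points. V/F = 100 L and an absorption rate of 1.5 per h are assumptions.

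| Half-life | AUC0-inf (mg·h/L) | CL/F (L/h) | Printed formula (L/h²) | Division by Kel (L) |
|---|---|---|---|---|
| 24 h | 112.37 | 2.848 | 0.082 | 98.6 |
| 20 h | 93.95 | 3.406 | 0.118 | 98.3 |

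Division recovers the 100 L put in to within 2%; the shortfall is trapezoid error in the AUC. The printed formula does not recover it. Repeating with V/F of 50, 200 and 400 L leaves the factor between the two formulas unchanged (about 1,199 and 833).

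**The case against.** The best defence is that this is a slip of notation. The printed line contains the same symbols as the correct one and differs only in where the bracket closes. The quantity is named correctly, and CL/F, Kel and t1/2 are all defined correctly. PK software would probably return the right volume whatever the protocol says. Section 14.3 lets the SAP modify the protocol's plans, and the SAP is not at hand, so the line may already be corrected there. All of this bears on how likely the harm is. It does not make the rule right: if the software is correct, the reported values do not follow the protocol's stated method.

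The illustrations also have limits, and these stand. The 20 h half-life comes from patients, in a study whose sampling was too short to characterise AUC0-inf, whereas this trial enrols only healthy subjects. The 1.44 therefore illustrates the algebra and is not an estimate of between-subject distortion here. Section 8.2.2 does not say that volume stayed constant as clearance fell. If CL/F fell because bioavailability rose, Kel would not change, true Vz/F would fall as well, and the printed formula would give the correct ratio between doses. The apparent falls in Step 4 are conditional on constant volume.

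Finally, Vz/F has no planned test or decision rule in the protocol, so the reach of the error is small.

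**Conclusion.** The formula is wrong as written. The dimensional contradiction follows from Section 13.3.3 alone and needs no assumption: the printed expression is CL/F × Kel, in volume per time squared, and equals the correct Vz/F multiplied by the subject's own Kel².

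The reach is narrow. Only Vz/F is affected. The primary safety objective, escalation, dose selection and the other nine PK parameters do not depend on it, and correct values can be recovered from reported CL/F and Kel. The harm arises only if the line is programmed literally. It should still be corrected, because the protocol fixes this endpoint definition itself and does not leave it to the SAP.

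**What to change.** In Protocol Section 13.3.3, define Vz/F as Dose/(AUC0-inf × Kel), equivalently (CL/F)/Kel, and state the same expression in the SAP before the PK analysis is programmed. If any output already exists, check that Vz/F is reported in a unit of volume and equals CL/F divided by Kel for each subject.

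The cost is one line of wording. Dosing, sampling and data collection do not change.
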